### **7.3.4 Replacement of patients**

Patients withdrawn by protocol deviation will be replaced by new patients until the expected number of patients. Patients withdrawn by other reasons will not be replaced.

## **7.4 PRE-RANDOMIZATION / PRE-BASELINE LOSSES**

Data from patients that do not meet the selection criteria after completing the screening visit will not be considered for the study. These data will not be collected.

## **8 TRIAL CONDUCTION AND RESPONSE EVALUATION**

### **8.1 CRITERIA FOR RESPONSE EVALUATION**

#### **8.1.1 Primary parameter**

Bacterial richness (observed species)\*.

#### **8.1.2 Secondary parameters**

- Gut bacterial composition\*
- Gut bacterial function\*
- Other estimators of richness and diversity: Chao1, ACE, Shannon, 1/Simpson.
- Inflammation: IL-6, IP-10
- Coagulation: D-Dimer
- Enterocyte damage: Intestinal Fatty Acid Binding Protein (I-FABP)
- Bacterial translocation and monocyte activation: LPS-binding protein (LBP), soluble CD14.
- Maturation, activation, exhaustion and immune senescence in CD4+ and CD8+ T-cells: CD3+, CD4+, CD8+, CD45RA, CCR7, CD28, CD27, HLA-DR, CD38, PD-1, CD57.\*\*
- CD4 and CD8+ counts
- CD4+/CD8+ ratio
- In case of changes in the microbiome, the quantification of viral reservoir will be done in PBMCs.

#### **\*Analysis of the composition, structure and function of the intestinal microbiome.**

- Structure and composition of the microbiome. DNA will be extracted and purified from fecal samples using the PowerSoil ® kit (MOBIO Laboratories, Carlsbad, USA) and cryopreserved at -80°C until amplification. The purified DNA will be amplified using Illumina-tagged primers to amplify the V3 and V4 16S ribosomal DNA (rDNA) regions, as described elsewhere [7,8]. PCR reactions will be performed in triplicate to preserve diversity. Pooled triplicates will be sequenced in a MiSeq platform, which will produce more than 30.000 sequences per each 16S measurement, ensuring adequate sampling depth. Bioinformatic analyses will be performed with the latest versions of the most frequently used pipelines. For example, 16S rDNA sequences will be analyzed with MOTHUR or equivalent software. The analysis procedure will include filtering sequences of poor quality, sequencing error correction, elimination of artifact chimeric sequences with UCHIME, taxonomic clustering of sequences, establishment of operational taxonomic units (Operative Taxonomic Units, OTU) and classification and annotation of OTUs using algorithms described in the Greengenes or SILVA databases. This will result in a detailed description of the composition of the intestinal bacteriome, including the relative abundance of the species detected.
- Function of the bacteriome. The software PICRUSt [5] will be used to predict the gene content and their corresponding functions. The gene content will be inferred from the abundance of each bacteria in the intestinal bacteriome according to the 16S rDNA information. PICRUSt has demonstrated excellent correlation with more costly and computationally intensive shotgun metagenomics approaches. Samples will be stored, however, to allow potential future metagenomics studies, not budgeted in this proposal.

#### **\*\*immune markers**

- Plasma markers will be assessed by Luminex and or ELISA technology using EDTA-plasma samples. PBMC-associated markers will be analyses using multicolor flow cytometry. In all cases cryopreserved samples, will be stained and acquired on a Fortesa (BD Biociences) cytometer and analyzed using commercial (Flow Jo) and on-site developed software (Ourflow).

## 8.2 TRIAL DEVELOPMENT

After accepting the participation and meeting selection criteria during the screening visit, patients would be assessed the baseline visit. Study visits would be at screening, entry (BL) and weeks 12, 24 and 48. Visits should be performed within a 2-weeks window.

Blood and fecal specimens will be obtained and stored at the points specified in the flow chart of the study.

Plasma samples and PBMC will be stored at -80°C.

Viral load, CD4 cells count and a complete biochemistry and hematology will be performed at all visits.

## 8.3 CLINICAL RECORD AND PHYSICAL EXAM

Demographic and HIV infection-related data will be collected in order to characterize the study population: sex, age, time since HIV diagnosis, risk factor and history of opportunistic infections or tumors, active acute or chronic diseases related or not with HIV-infection, date and type of past surgical interventions, ART history, nadir and current CD4+ counts, HBV or HCV co-infection, history of HPV infection, allergies, current abdominal transit, history of altered abdominal transit, current or past antibiotic therapy, dosing and duration of antibiotic therapy during the previous 6 months.

Patients will be asked for all medication, antiretroviral or not, that he/she may have taken (including over the counter medication), within one week before inclusion and during the study.

A complete physical examination will be performed at the baseline visit, including weight and height. In the follow-up, a physical exam will be performed according to patient's symptoms.

## 8.4 LABORATORY TESTS

Patients will fast for at least 8 hours prior to assessment, in the points specified in the flow chart of the study (section 8.5). The following parameters will be quantified, as needed:

- **Blood count:**
  - Hemoglobin
  - Red blood count
  - Hematocrit
  - White cell blood count
  - Neutrophil count
  - Lymphocyte count
  - Platelets
  - Prothrombin time
- **Blood biochemistry:**
  - Albumina
  - Glucose
  - Urea
  - Creatinine
  - Estimated glomerular filtration rate (CKD-EPI)
  - Ionogramme: sodium, potassium
  - Total Bilirubin
  - Cholesterol (HDL, LDL and total)
  - Triglycerides
  - Liver enzymes: aspartate aminotransferase (AST), alanine aminotransferase (ALT), gamma-GT, alkaline phosphatase
- **Pregnancy test in women (test strip)**

- **Immunology:**
  - CD4 lymphocytes count
  - CD4 lymphocytes percentage
  - CD8 lymphocytes count
  - CD8 lymphocytes percentage
  - CD4/CD8 ratio
  - HLA-DR
- **Virology:** Plasma HIV-1 viral load.
- **Genotypic testing in plasma at virological failure.**
- **Whole blood:** a blood sample (5 x 10 mL EDTA tubes will be collected at each visit, from which irsiCaixa will obtain 4 plasma vials and as many PBMCs as possible). Plasma markers will be assessed by Luminex and or ELISA technology using EDTA-plasma samples. PBMC-associated markers will be analyses using multicolor flow cytometry. In all cases cryopreserved samples, will be stained and acquired on a Fortesa (BD Biociences) cytometer and analyzed using commercial (Flow Jo) and on-site developed software (Ourflow). In case of changes in the microbiome, the quantification of viral reservoir will be done in PBMCs.
- **Stool samples** will be collected at each visit. This will allow accounting for natural variation in gut microbiota composition. Samples will be used for taxonomic and functional / metagenomic analysis of the bacterial and viral microbiome and soluble & cellular markers of immune activation, inflammation and bacterial translocation.

**Note: Before the beginning of the study, all labs will facilitate to the sponsor and to the investigator a list of the reference normal values of the parameters assessed.**

## 8.5 ASSESSMENTS FLOW-CHART

VISITS	SCR	BL	W12	W24	W48	VF
Window			+/- 2 weeks	+/- 2 weeks	+/- 2 weeks	
Inclusion/exclusion criteria	✓					
Patient informed form and Informed consent	✓					
Pregnancy test	✓ B			✓		
Randomization		✓				
Clinical visit		✓	✓	✓	✓	
Adherence questionnaire		✓	✓	✓	✓	
HIV-1 Viral load	✓ C	✓	✓	✓	✓	✓
Biochemistry	✓ C	✓ C	✓	✓	✓	
Hematology	✓ C	✓ C	✓	✓	✓	
CD4/CD8 cells count		✓ C	✓	✓	✓	
Stool sample		✓	✓	✓	✓	
Whole blood simple for IRSIA		✓	✓	✓	✓	
Adverse Events		✓	✓	✓	✓	
Concomitant medication		✓	✓	✓	✓	
Genotypic testing						✓

A **blood sample** (5 x 10 mL EDTA tubes, from which irsiCaixa will obtain 4 plasma vials and as many PBMCs as possible)

B Women of childbearing potential, within 10 days prior to randomization.

C Parameters performed within 2 months prior to Baseline will be accepted.

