### 6.3 DOSE, INTERVAL, ROUTE AND METHOD OF ADMINISTRATION

The route of study drug administration is oral.

- Reformulated Raltegravir 1200 mg (2 tablets at the same time x 600mg) once daily plus current ART during 48 weeks from randomization.
- RAL- Placebo (2 tablets at the same time of placebo) once daily plus current ART during 48 weeks from randomization.

Reformulated raltegravir/placebo can be taken with or without food.

If a subject misses a dose and it is less than 12 hours before the next dose, the missed dose should be skipped and the normal dosing schedule resumed. The subject should not double the next dose in order to compensate for what has been missed.

Acceptable antiretroviral drugs in the background regimen will include a PI boosted with cobicistat/ritonavir or NNRTI/NRTI based 3-drug ART.

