### 9.2 MONITORING, RECORDING AND REPORTING OF ADVERSE EVENTS

An AE is any noxious, unintended, or untoward medical occurrence that may appear or worsen in a subject during the course of a study. It may be a new intercurrent illness, a worsening concomitant illness, an injury, or any concomitant impairment of the subject's health, including laboratory test values (as specified by the criteria below), regardless of etiology. Any worsening (i.e., any clinically significant adverse change in the frequency or intensity of a pre-existing condition) should be considered an AE. A diagnosis or syndrome should be recorded on the AE page of the CRF rather than the individual signs or symptoms of the diagnosis or syndrome.

An overdose, accidental or intentional, whether or not it is associated with an AE, or abuse, withdrawal, sensitivity or toxicity to an investigational product should be reported as an AE. If an overdose is associated with an AE, the overdose and AE should be reported as separate terms.

All subjects will be monitored for AEs during the study. Assessments may include monitoring of any or all of the following parameters: the subject's clinical symptoms, laboratory, pathological, radiological or surgical findings, physical examination findings, or other appropriate tests and procedures.

All AEs will be recorded by the Investigator from the time the subject signs informed consent until the last study visit or to 28 days after the last dose of IMP in case of early withdrawal while patient is receiving IMP. AEs and SAEs will be recorded on the AE page of the eCRF and in the subject's source documents. All SAEs must be reported to the Sponsor (see contact details at the end of the paragraph) within 24 hours of the Investigator's knowledge of the event by facsimile, or other appropriate method, using the SAE Report Form (Appendix IV, can be found in the Investigator's File), or approved equivalent form.

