#### **9.7 PREGNANCY**

The cases of pregnancy shall be recorded as AE and should only be considered as SAE only if they meet any seriousness criteria. Pregnancy is also a protocol deviation requiring premature termination of the patient. The investigator will provide medical support to the pregnant patient.

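### Minor safety improvement: the only scheduled on-treatment pregnancy test is at week 24; strips at the existing week 12 and week 48 visits would cut the longest untested stretch before week 24 from 27.4 to 16 weeks and add an end-of-treatment test

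*Combined protocol and SAP*

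**What the plan says.** **Schedule.** The Section 8.5 flow-chart has one row for the pregnancy test. It is ticked at screening, with the footnote "Women of childbearing potential, within 10 days prior to randomization", and at week 24. The cells for baseline, week 12, week 48 and virological failure are empty. No section in the visible text sets a test frequency.

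**Visits and dosing.** Study drug is taken "once daily plus current ART during 48 weeks from randomization" (Section 6.3). Section 8.2 states: "Study visits would be at screening, entry (BL) and weeks 12, 24 and 48". The three on-treatment visits each have a window of 2 weeks either side (Section 8.5) and include a clinical visit, adverse event review and concomitant-medication review.

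**Testing at discretion.** Section 8.4 lists a strip pregnancy test for women under the lead-in "The following parameters will be quantified, as needed". Section 9.2 lets adverse event monitoring draw on "physical examination findings, or other appropriate tests and procedures".

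**Consequences of a pregnancy.** Section 7.2 excludes pregnant women and requires effective contraception from baseline to the end of the trial. Section 9.7 states: "The cases of pregnancy shall be recorded as AE", and also: "Pregnancy is also a protocol deviation requiring premature termination of the patient".

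**End of recording.** Under Section 9.2 adverse events are recorded "until the last study visit or to 28 days after the last dose of IMP in case of early withdrawal". The 28-day extension is for early withdrawals, so a completer's recording closes at her last visit.

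**The concern.** The protocol's own rules call for a pregnancy to be found, recorded and followed by the end of study participation. The schedule supports those rules with one planned test in 48 weeks of dosing. Two situations are poorly covered.

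- A woman without symptoms who conceives soon after randomisation may continue study drug until the week 24 test, although Section 9.7 would end her participation once the pregnancy was known.
- A woman who conceives after week 24 can complete the trial with no further scheduled test before adverse event recording closes. The exposure may then never enter the trial record.

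Follow-up physical examination depends on symptoms (Section 8.3), so it is not a routine backstop. The product is a formulation that is not yet marketed (Section 6.1). What is at stake is participant safety and completeness of safety data; the primary endpoint, blinding and analysis are not affected.

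**Working it through.** The documents give no figure for the interval between tests, so there is none to reproduce. The check is interval arithmetic on the schedule.

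**Inputs**
- Pre-randomisation test: 0 to 10 days before randomisation, that is 0 to 10/7 = 1.43 weeks (Section 8.5, footnote B).
- Visits at weeks 12, 24 and 48, each plus or minus 2 weeks (Section 8.5).
- Assumption: randomisation takes place on the baseline day, where Section 8.5 ticks it.

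**Formulas**
- Shortest interval between two visits: (later − 2) − (earlier + 2). Longest: (later + 2) − (earlier − 2).
- From the pre-randomisation test to a visit: shortest is visit − 2 + 0; longest is visit + 2 + 1.43.

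**Results, in weeks**

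| Interval | Shortest | Longest | Nominal (visits on time) |
|---|---|---|---|
| Now: pre-randomisation test to week 24 | 24 − 2 = 22 | 24 + 2 + 1.43 = 27.4 | 24 to 25.4 |
| With week 12 strip: pre-randomisation test to week 12 | 12 − 2 = 10 | 12 + 2 + 1.43 = 15.4 | 12 to 13.4 |
| With week 12 strip: week 12 to week 24 | 22 − 14 = 8 | 26 − 10 = 16 | 12 |
| Week 24 to week 48 (no visit between) | 46 − 26 = 20 | 50 − 22 = 28 | 24 |

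**Effect before week 24.** The longest untested stretch becomes max(15.4, 16) = 16 weeks. The fall is 27.43 − 16 = 11.43 weeks, and 11.43/27.43 = 42%.

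**Effect after week 24.** At present no test follows week 24. A week 48 strip would close that stretch, but its length stays at 20 to 28 weeks.

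**Number of tests.** Scheduled tests go from 1 of 3 to 3 of 3 on-treatment visits. The added strips number 2 per woman of childbearing potential. The documents do not give the number of such women, so the range is 2 × 0 = 0 to 2 × 60 = 120, the ceiling assuming that all 60 participants qualify. For the same reason the number of exposed pregnancies cannot be estimated.

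**The case against.** The strongest reply is that this is a preference, not a defect. The protocol has a recent test before randomisation, a mid-treatment test, mandatory contraception in which condoms alone do not count, and a rule for handling pregnancy. Nothing in the documents says that one on-treatment test is too few. The Investigator's Brochure and the patient information appear only as appendix titles, and either might carry further instructions. All of this stands, and it is why the point is rated minor and claims no breach. It does not change what Section 8.5 schedules.

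Second, testing is already possible at weeks 12 and 48 under Sections 8.4 and 9.2, and a missed period could prompt it. That is true, but discretionary testing depends on suspicion, and the gap concerns women who give no cause for it.

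Third, the gain is partial. Over the whole trial the longest interval ending in a scheduled test would be week 24 to week 48, up to 28 weeks, and no existing visit shortens it. The 27.4 and 16 week figures are window extremes. Dosing ends at 48 weeks, so a strip at that visit records exposure without preventing it, and a pregnancy first recognised later would still fall outside adverse event recording. These limits stand in full. They leave the gain before week 24 intact, and the week 48 test remains the last scheduled chance to record an exposed pregnancy in a completer.

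**Conclusion.** The point holds as a low-priority safety improvement that the sponsor could adopt. Section 8.5 schedules one pregnancy test during 48 weeks of dosing, although two further visits are available for it. Adding week 12 reduces the longest untested stretch before week 24 from 27.4 to 16 weeks (from 24 to 25.4 down to 12 to 13.4 when visits fall on time). Adding week 48 provides an end-of-treatment test where none is scheduled. The figures rest on randomisation at the baseline visit and on the stated windows. Contraception under Section 7.2 remains the main control. How many women would benefit is unknown.

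**What to change.** In the pregnancy-test row of Section 8.5, add ticks at week 12 and week 48 for women of childbearing potential, using the strip already listed in Section 8.4. Optionally, add a note at baseline that the footnote B test is done there when the screening test is more than 10 days old; this only clarifies the layout.

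The cost is at most 2 extra strips per woman of childbearing potential (0 to 120 in all) and no new visit. A numbered, dated amendment is needed (Section 1.3). The documents do not say what ethics committee or drug agency review such a change would require, so it is best bundled with any other amendment.

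The change does not shorten the 20 to 28 weeks between weeks 24 and 48. That would take a test between visits, for example a home strip near week 36, which goes beyond the low-cost change proposed here.

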## 9 ADVERSE EVENTS

### 9.1 DEFINITION

**Adverse event:** (AE) Medical event presented by a patient or clinical research subject administered a pharmaceutical product, and which does not necessarily have a causal relation to the treatment.

**Serious adverse event:** (SAE) Medical event classified as such and which, regardless of the dose involved:

- causes patient death,
- produces a life-threatening situation for the patient,
- requires or prolongs in hospital admission,
- produces important or persistent incapacitation/handicap, or constitutes a congenital defect or anomaly,
- needs action to prevent any of above situations, or
- is considered medically significant

Examples of such events are intensive care in an Emergency Service or in the home in a patient with allergic bronchospasm; blood dyscrasias or seizures not giving rise to hospital admission, or the development of drug dependency or abuse.

**Unexpected adverse event:** (UAE) AE related to the product in investigation the nature or intensity of which does not coincide with the information available on the product administered (IB or SmPC).

**Serious Unexpected Adverse Reaction:** (SUSAR) SAE related to the product in investigation the nature or intensity of which does not coincide with the information available on the product administered (IB or SmPC).

### 9.2 MONITORING, RECORDING AND REPORTING OF ADVERSE EVENTS

An AE is any noxious, unintended, or untoward medical occurrence that may appear or worsen in a subject during the course of a study. It may be a new intercurrent illness, a worsening concomitant illness, an injury, or any concomitant impairment of the subject's health, including laboratory test values (as specified by the criteria below), regardless of etiology. Any worsening (i.e., any clinically significant adverse change in the frequency or intensity of a pre-existing condition) should be considered an AE. A diagnosis or syndrome should be recorded on the AE page of the CRF rather than the individual signs or symptoms of the diagnosis or syndrome.

An overdose, accidental or intentional, whether or not it is associated with an AE, or abuse, withdrawal, sensitivity or toxicity to an investigational product should be reported as an AE. If an overdose is associated with an AE, the overdose and AE should be reported as separate terms.

All subjects will be monitored for AEs during the study. Assessments may include monitoring of any or all of the following parameters: the subject's clinical symptoms, laboratory, pathological, radiological or surgical findings, physical examination findings, or other appropriate tests and procedures.

All AEs will be recorded by the Investigator from the time the subject signs informed consent until the last study visit or to 28 days after the last dose of IMP in case of early withdrawal while patient is receiving IMP. AEs and SAEs will be recorded on the AE page of the eCRF and in the subject's source documents. All SAEs must be reported to the Sponsor (see contact details at the end of the paragraph) within 24 hours of the Investigator's knowledge of the event by facsimile, or other appropriate method, using the SAE Report Form (Appendix IV, can be found in the Investigator's File), or approved equivalent form.

### 9.3 DOCUMENTATION RELATED TO AE AND SAE

Each AE and SAE to take place during the study should be documented in the medical records of the subject in accordance with standard clinical practice of the researcher, and in the CRF. For each SAE, an independent set

of SAE forms will be used. Only if there are multiple SAE at the time of the initial report and these are temporary and / or clinically interrelated can they be registered on the same set of SAE forms.

The researcher should try to make a diagnosis of the event based on the signs, symptoms and / or other clinical information. An AE diagnosis has to be recorded per line or a sign/symptom if the diagnosis is not available. If a diagnosis subsequently becomes available, this then should be entered and the sign/symptom crossed out, initialed and dated by the investigator.

SAE pages found in the investigator's file shall be completed as precisely as possible, printed and shall be signed by the investigator before being sent to the sponsor. It is very important that the researcher completing the SAE form provides their opinion in regard to the relationship of the event to the study drug.

## **9.4 EVALUATION OF ADVERSE EVENTS**

### **9.4.1 Description of the imputability criteria**

Relatedness is an assessment made by a study clinician of whether or not the event is related to the study agent. Degrees of relatedness will be categorized according to current DAIDS-approved guidelines (Appendix V). Per the Manual for Expedited Reporting of Adverse Events to DAIDS (Version 2.0, January 2010), the relationship categories that will be used for this study are:

Related: There is a reasonable possibility that the AE may be related to the study agent(s) suggested by:

- A plausible, reasonable time sequence exists in relation to administration of the drug or its plasma or tissue concentrations.
- The observed manifestation coincides with the known adverse reactions profile of the implicated drug.
- The event cannot be or unlikely be explained by a concurrent disease or by other drugs or chemical substances.
- Response to withdrawal is clinically plausible, i.e., the condition improves on discontinuing administration of the drug.

Not Related: There is not a reasonable possibility that the AE is related to the study agent(s).

